## 5.3 Echocardiographic, Clinical, and Functional Endpoints and Parameters

### 5.3.1 Echocardiographic Endpoints and Parameters

A. Reduction in TR severity (assessed by TR grade and quantitative measures) as assessed by TEE pre- and post-implant in the procedure room.

Additional echocardiographic parameters will be compared to baseline:

B. TTE parameters assessed at baseline, discharge, 30 days, 6 months, 1 year and annually until 5 years post procedure:

1. TR grade
2. Vena Contracta (2D)
3. EROA (PISA/2D or 3D/3D color Doppler)
4. Regurgitant volume
5. Tricuspid annular dimensions
6. TV inflow gradient
7. Cardiac output
8. Right ventricle dimensions
9. Right atrium volume
10. Left ventricular Ejection Fraction
11. Inferior Vena Cava dimensions/respiratory variations
12. Hepatic vein flow reversal
13. Pulmonary artery pressure (mean)
14. Right ventricular function

---

\* The TR grading scale used to determine procedural success is based on the scale proposed by Hahn and Zamorano (scale: none/trace, mild, moderate, severe, massive, torrential), while patient eligibility is based on the grading scale presented in the current ASE guidelines (Zoghbi et al., JASE 2017).

### 5.3.2 *Clinical and Functional Endpoints and Parameters*

**Clinical and Functional Endpoints** – assessed at baseline and at various time points, depending on the parameter (see Table 11)

- A. All-cause mortality
- B. Heart failure hospitalizations
- C. Unplanned or emergency re-intervention (either percutaneous or surgical) related to the device
- D. Volume overload assessed by serial measurements of:
  - 1. Body weight
  - 2. Edema assessment (1+ to 4+)
  - 3. Ankle circumference measurement
  - 4. Patient edema questionnaire
- E. Quality of life and functional status assessed by:
  - 1. NYHA Classification
  - 2. 6-Minute Walk Test (6MWT)
  - 3. KCCQ
  - 4. Short Form Health Survey (SF-36)

### **Clinical and Functional Parameters**

- A. Baseline Canadian Study of Health and Aging (CSHA) Clinical Frailty Scale
- B. Baseline Katz Index of Independence in Activities of Daily Living (Katz ADL)
- C. Baseline Patient Preference Survey
- D. Electronic Diary (eDiary)\*: Administered via a handheld device as follows:
  - 1. Baseline: Question(s) from PROMIS Mood questionnaire, Visual Analog Scale (VAS), and KCCQ-12 will be administered daily for a minimum of 2 weeks before the index procedure and then paused at time of admission for index procedure.
  - 2. Post discharge: Starting post discharge, question(s) will be administered daily for 7 days, every other week, to the 12-month follow-up visit.
  - 3. 12-month follow-up visit: Starting at the 12-month follow-up visit, question(s) will be administered daily for a week, up to 7 days.

---

\* eDiary and Activity Monitoring to be implemented at system launch. Patients enrolled prior to system launch will not be required to participate in these assessments.

- E. Activity Monitoring\*: Administered via a wearable monitor as follows:
  - 1. Baseline: Activity monitoring will occur for a minimum of 2 weeks before the index procedure and then paused at time of admission for index procedure
  - 2. 30 days post discharge
  - 3. 2 weeks at 3 months, 6 months, 9 months, and 12 months post index procedure.
- F. General Clinical and Laboratory Parameters assessed by:
  - 1. Creatinine, BUN, uric acid, and eGFR
  - 2. Liver Panel (Albumin, Bilirubin, ALP, ALT, AST, GGT)
- G. Diuretic medications and doses (No change in current or new addition to diuretics are allowed for at least 3 months post procedure unless medically required, i.e. severe hypotension, or signs and symptoms of hypervolemia.)

### **5.3.3 Additional Safety Assessments**

In addition to the above endpoints and parameters, a listing of all the AEs and SAEs for the entire study population will be provided.

## **6 STUDY DESIGN**

This is a prospective, single arm, multi-center, early feasibility study designed to evaluate the safety and performance of the PASCAL System in the treatment of symptomatic severe tricuspid regurgitation (TR).

Up to 65 patients (pending FDA approval) will be enrolled in the study at up to 30 investigational sites (pending FDA approval) in the US. All enrolled study patients will be assessed for clinical follow-up at the following intervals: discharge, 30 days, 6 months, 1 year, and annually for 5 years post implant procedure.

A description of each study visit and required study procedures are included in Section 8, Procedures and Methods. In addition, a summary of required procedures is listed in Table 11.

## **7 PATIENT POPULATION**

### **7.1 Demographic and Clinical Characteristics**

This clinical study is for adult patients with symptomatic severe tricuspid regurgitation who are deemed to be appropriate potential candidates for transcatheter tricuspid repair with the PASCAL System as assessed by the Heart Team.

This study is expected to enroll patients with similar baseline characteristics to previously studied populations of percutaneous TR interventions. The mean age of the first-in-human compassionate use experience with the Edwards PASCAL device in the treatment of patients with severe TR was  $78 \pm 5$  years, and we expect that this EFS will enroll patients with the same baseline characteristics. Additionally, patients that received the Edwards Cardioband Tricuspid Valve Reconstruction System as part of the European TRI-REPAIR study were on average  $75.6 \pm 6$  years of age. Although those patients were not treated with the Edwards PASCAL System, we expect that this EFS will enroll patients with similar baseline characteristics as those studied under the TRI-REPAIR protocol, as well. Therefore, we expect that participants will qualify for Medicare coverage through the age criteria and we anticipate that the results of this study will be generalizable to the Medicare population.

All patients who meet the initial study eligibility requirements will be evaluated for study participation.

Candidates for this study must meet all of the following inclusion criteria and none of the exclusion criteria.

## 7.2 Inclusion Criteria

Patients enrolled must meet ALL of the following criteria:

1. Age  $\geq 18$  years old
2. Symptomatic despite optimal medical therapy per local Heart Team
3. Functional or degenerative TR graded as severe\* as assessed by the echo core lab
4. The local site Heart Team determines that the patient is appropriate for transcatheter tricuspid valve repair
5. Patient is willing and able to comply with all specified study evaluations and provides written informed consent.

## 7.3 Exclusion Criteria

Potential patients will be excluded if ANY of the following criteria apply:

1. Echocardiographic parameters (any of the following):
  - a. Tricuspid valve anatomy precluding proper device deployment and function, including:

---

\* The TR grading scale used to determine procedural success is based on the scale proposed by Hahn and Zamorano (scale: none/trace, mild, moderate, severe, massive, torrential), while patient eligibility is based on the grading scale presented in the current ASE guidelines (Zoghbi et al., JASE 2017).

- i. Evidence of severe calcification in the annulus or subvalvular apparatus
    - ii. Evidence of moderate to severe calcification in the grasping area
    - iii. Excessive chordae structure in the grasping area
    - iv. Presence of perforation in the grasping area
    - v. Leaflet length < 8 mm
    - vi. Septo-lateral coaptation gap > 10 mm
    - vii. Severe leaflet tethering or immobile leaflet
  - b. LVEF < 30%
  - c. Severe right ventricular dysfunction as assessed by the core lab
2. Primary non-degenerative tricuspid disease (e.g. carcinoid, rheumatic, endocarditis, traumatic, pacemaker lead-induced, iatrogenic, tricuspid stenosis)
  3. Previous tricuspid valve repair or replacement that would interfere with placement of PASCAL.
  4. Presence of trans-tricuspid pacemaker or defibrillator leads which:
    - a. Would prevent proper TR reduction due to interaction of the lead with the leaflets
    - b. Were implanted in the RV within the last 3 months
  5. Severe aortic, mitral and/or pulmonic valve stenosis and/or regurgitation
  6. Active endocarditis within 3 months of the scheduled implant
  7. Hemodynamically significant pericardial effusion
  8. Intra-cardiac mass, thrombus, or vegetation
  9. Untreated clinically significant coronary artery disease requiring revascularization
  10. MI or known unstable angina within 30 days prior to the index procedure
  11. Any invasive cardiac procedure within 30 days prior to the index procedure
  12. Any cardiac surgery within 3 months prior to procedure
  13. Suspicion of pericardial adhesions that may preclude leaflet approximation (e.g. post pericarditis, constrictive pericarditis, calcifications visible on imaging)
  14. Hemodynamic instability or on IV inotropes unless part of prehabilitation
  15. Severe uncontrolled hypertension (SBP  $\geq$  180 mmHg and/or DBP  $\geq$  110 mmHg)
  16. Pulmonary systolic pressure > 60 mmHg as assessed by echo core lab
  17. Stroke or transient ischemic attack (TIA) within the past 30 days
  18. Kidney dysfunction with estimated Glomerular Filtration Rate (eGFR)  $\leq$  30 mL/min/1.73 m^2 or patient is on chronic dialysis

19. Any physical impairment which limits the patient's capacity to complete functional testing due to other medical conditions independent of their TR (e.g. orthopedic condition)
20. Significant frailty (i.e. Katz Index of Independence in Activities of Daily Living (ADL)  $\leq 2$ ) within 3 months of scheduled implant
21. Continuous home oxygen for primary severe COPD
22. Chronic anemia (Hgb  $< 9$  g/dL) not corrected by transfusion
23. Thrombocytopenia (Platelet count  $< 100,000/\text{mm}^3$ ) or thrombocytosis (Platelet count  $> 750,000/\text{mm}^3$ )
24. Bleeding disorders or hypercoagulable state
25. Active peptic ulcer or active gastrointestinal (GI) bleeding within 3 months of the scheduled implant
26. Contraindication to anticoagulants or antiplatelet agents
27. Current, or history of, IV drug use
28. Pregnant or lactating; or female of childbearing potential with a positive pregnancy test 24 hours before any study-related radiation exposure
29. Patients in whom transesophageal echocardiography is contraindicated.
30. In the opinion of the investigator, access to the femoral vein with a 22 FR guide is deemed not feasible (e.g. IVC filter, DVT, occluded femoral veins).
31. Untreatable hypersensitivity or contraindication to any of the following:
  - a. Aspirin and Clopidogrel and Ticlopidine
  - b. Heparin and Bivalirudin, or Warfarin
  - c. Nitinol Alloys (Nickel and Titanium)
  - d. Contrast media
32. Currently participating in another investigational biologic, drug or device study that has not completed the primary endpoint or that clinically interferes with the endpoints of this study.
33. Co-morbid condition(s) that, in the opinion of the Investigator, limit life expectancy to  $< 12$  months.
34. Presence of significant congenital heart disease including but not limited to atrial septal defect, RV dysplasia, and arrhythmogenic RV.
35. Co-morbid condition(s) that, in the opinion of the investigator, could limit the patient's ability to participate in the study, including compliance with follow-up requirements, or that could impact the scientific integrity of the study.
36. Patient is under guardianship.

## 7.4 Study Exit Criteria and Procedures

The reason for study exit will be documented on the appropriate case report forms and in the medical records for each patient who exits the study.

Patients may exit the study for any of the following reasons:

- Screen Failure
- Study Device Attempted But Not Implanted
  - Enrolled patients for whom the implant procedure was prematurely aborted (e.g., entered procedure room and anesthesia induced, but study procedure not attempted (i.e. skin incision to introduce the PASCAL System) or TTVr procedure attempted but did not receive a study device, will be followed for 30 days for safety evaluations only or until resolution of any adverse events related to the implant procedure and then exited from the study.
- Study Device Re-intervention/Explant
  - Patients who have a surgical re-intervention where the device is explanted will be followed for 30 days post-re-intervention for safety evaluations only or until resolution of any adverse events related to the re-intervention and then exited from the study. Patients who have a percutaneous re-intervention where the study device remains in place will continue to be followed for the duration of the study.
- Completion per Protocol
- Withdrawal
  - Patient Withdrawal: The patient may voluntarily withdraw from the clinical study at any time, without penalty or loss of benefits to which they are otherwise entitled.
  - Physician Withdrawal: The Investigator also has the right to withdraw a patient if s/he feels it is in the best interest of the patient to do so.
- Death
- Lost to Follow-up
  - If a patient cannot be reached for a follow-up visit, the Investigator will document the contact efforts made to the patient and/or effort to obtain hospital records in the appropriate electronic case report form. If the patient cannot be reached in any way, or misses a visit, the patient will be considered “unable to contact” for that time interval. After three (3) documented unsuccessful attempts to make contact prove unsuccessful, a certified letter will

be sent to the patient's residence. If there is no response after the certified letter is sent, the patient will be considered "lost to follow-up".

- For patients who are lost to follow-up or withdraw early, Sponsor may request the site to search the Social Security Death Index and/or other death registries and may request the site to obtain the death certificate, if applicable.
- In all cases of withdrawal (as described above), withdrawn patients will not undergo further study follow-up procedures after the time of study exit. A study patient who has been withdrawn from the study will not be replaced.
- All data collected up until the time of withdrawal, including imaging studies such as echocardiography scans, will be analyzed in encrypted form and will be kept in encrypted form for the entire duration of the study.

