## 11.2 AE Reporting Requirements

The Investigator will report all adverse events to the Sponsor as soon as possible, but no later than 10 working days after the Investigator first learns of the event.

Each adverse event must be reported on a separate AE CRF. In the event that the EDC system is not in service or otherwise not accessible, the Sponsor must be notified by email [REDACTED]. The AE CRF should be completed as soon as possible thereafter.

At the time of initial notification, the following minimal information must be provided:

- Study site number
- Patient ID number
- Site's awareness date
- AE description
- Causal relationship to device and implant procedure, if known

The site will provide the Sponsor copies of relevant supporting source documentation (e.g. admission H&P, implant procedure report, discharge summary, echocardiogram and laboratory results) for all adverse events requiring CEC adjudication (at a minimum, safety endpoints) and those events determined by the Sponsor to require additional investigation.

Adverse events must be followed until resolution, the patient is lost to follow-up, the patient has withdrawn consent, or the adverse event is otherwise explained.

The Investigator will inform their IRB and FDA of adverse events in accordance with the relevant local and regional regulatory requirements.

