## 11.8 Investigational Device Explants

An Edwards' study device that is explanted at any time with an allegation of device malfunction or deficiency, should be returned to the Sponsor for evaluation. All other explants should be discarded.

Once the study device is explanted, the patient is followed for 30 days after the explant, unless there is an ongoing related adverse event and its outcome is not deemed resolved by the Investigator. Patients will then be exited from the study once AE(s) resolved or 180 days post-explant, whichever comes first. Return kits for explanted devices will be provided upon request by the clinical monitor or study team.

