5.1.3 Last Information Date

 Edwards Lifesciences	Revision Date: January 22, 2019		Rev	For Use Only by Affiliates of Edwards Lifesciences	Page 14 of 25
	Title		Statistical Analysis Plan for Edwards CLASP TR EFS		

The last information date is defined as the latest date assessed with any available information concerning the patient (e.g., most recent date out of: baseline assessment, procedure, discharge, all follow-up visits, laboratory tests, and adverse events). Last information date is used as the censor date for survival analyses.

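### Patients who leave because the device failed or was explanted have no vital-status follow-up, so Kaplan-Meier mortality to 5 years rests on an unchecked assumption of non-informative censoring

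*Protocol*

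**What the plan says.** **Exit rules.** Protocol 7.4 states that patients in whom the procedure was attempted but no device was left in place "will be followed for 30 days for safety evaluations only or until resolution of any adverse events related to the implant procedure" and are then exited. Patients whose device is surgically explanted "will be followed for 30 days post-re-intervention for safety evaluations only or until resolution of any adverse events related to the re-intervention" and are then exited. By contrast, "Patients who have a percutaneous re-intervention where the study device remains in place will continue to be followed for the duration of the study".

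**Registry search.** Protocol 7.4 also states: "For patients who are lost to follow-up or withdraw early, Sponsor may request the site to search the Social Security Death Index" or other registries. Device not implanted, re-intervention/explant, withdrawal and loss to follow-up are separate exit categories in that section. Protocol 11 captures adverse events only until participation ends.

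**Planned follow-up.** Protocol 6 has all enrolled patients assessed annually to 5 years, and 8.4 defines enrolment as skin incision. Failed attempts are therefore enrolled patients.

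**Analysis.** All-cause mortality is a listed endpoint (Protocol 5.3.2). SAP 8.2.2 estimates it by Kaplan-Meier with Greenwood standard errors at 30 days, 6 months, 1 year and annually. SAP 5.1.3 adds: "Last information date is used as the censor date for survival analyses". SAP 6.2 uses available data without imputation. Protocol 12.5 leaves open a binary proportion as an alternative. No sensitivity analysis for early exits is planned, and neither document names the population for mortality.

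**Unresolved events after explant.** Protocol 11.2 says "Adverse events must be followed until resolution, the patient is lost to follow-up" or one of a few other end points is reached. Protocol 11.8 says "Patients will then be exited from the study once AE(s) resolved or 180 days post-explant, whichever comes first".

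**The concern.** Kaplan-Meier estimation is unbiased only if patients censored at a given time have the same later risk as those still followed. Here two groups are censored because the treatment could not be delivered or had to be removed. It is reasonable to suspect that their prognosis differs from that of patients with a working implant, and the plan collects nothing after exit that could confirm or refute this. A binary proportion on available data would not help, because the same patients would drop out of the denominator.

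What is at stake is a mortality estimate out to 5 years in a study that has guidance for future designs among its objectives. Once vital status has not been collected, the gap cannot be measured afterwards.

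**Working it through.** **1. No plan figure to reproduce.** The documents give no implant-failure, explant or expected mortality rate, and the text after the sample-size sentence is redacted. Only N = 65 (the maximum in Protocol 12.1) comes from the documents. The rates below are assumptions.

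**2. Who is affected, by analysis set.**

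| Group | ITT (skin incision) | As-treated (implant in position on leaving the room) |
|---|---|---|
| Attempted, not implanted | censored at exit | not in the set (selection, not censoring) |
| Surgically explanted later | censored at exit | censored at exit |
| No skin incision | not in the set | not in the set |

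**3. Illustrative model.** Let a share f exit at t0 = 30/365 years. Retained patients have 1-year mortality m, with constant hazard λ = −ln(1 − m). Exited patients have hazard HR × λ.

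- True survival: S_true(T) = (1 − f)·exp(−λT) + f·exp(−HR·λT)
- Kaplan-Meier target: S_KM(T) = [(1 − f)·exp(−λt0) + f·exp(−HR·λt0)]·exp(−λ(T − t0))

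Assumed ranges: f = 5-15% (about 3 to 10 of 65), m = 10-20%, HR = 1-3.

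Worked case with f = 0.15, m = 0.20, HR = 3, T = 1:

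- S_true = 0.85 × 0.80 + 0.15 × 0.80³ = 0.680 + 0.077 = 0.757, so true mortality is 24.3%.
- Survival to day 30 = 0.85 × 0.982 + 0.15 × 0.946 = 0.977. Then S_KM = 0.977 × 0.815 = 0.796, so Kaplan-Meier shows 20.4%.
- Understatement: 3.9 points.

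Understatement of 1-year mortality (percentage points):

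| m | f | HR 1 | HR 2 | HR 3 |
|---|---|---|---|---|
| 10% | 5% | 0 | 0.4 | 0.8 |
| 10% | 10% | 0 | 0.8 | 1.6 |
| 10% | 15% | 0 | 1.2 | 2.3 |
| 20% | 5% | 0 | 0.7 | 1.3 |
| 20% | 10% | 0 | 1.5 | 2.6 |
| 20% | 15% | 0 | 2.2 | 3.9 |

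If the same constant hazards held to 5 years, the gap would be 0 to 5.6 points. The largest is at f = 0.15, m = 0.10, HR = 3, with 46.7% true against 41.1% shown.

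**4. Sampling error for scale.** Half-width = 1.96·√(p(1 − p)/65). At p = 0.10 this is 7.3 points and at p = 0.20 it is 9.7 points.

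**5. Bounds without a hazard assumption.** Suppose 6 of 65 exit and 6 of the other 59 die by 1 year. The estimate is 6/59 = 10.2%. If none of the exited patients died it is 6/65 = 9.2%, and if all died it is 12/65 = 18.5%.

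**The case against.** The strongest reply is that this is a descriptive single-arm feasibility study whose safety and performance endpoints all end by 30 days, which the exit rules largely preserve. Long-term mortality is one descriptive endpoint among many, and the illustrated gap is smaller than the sampling error. That stands, and it limits the weight of the point. It does not remove it, because the gap arises from the design and does not shrink with more patients.

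Four stronger readings are tempting but not supported:

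- *That the censoring is shown to be informative.* The documents contain no outcome data for these patients. With equal hazards the bias is zero. That they do worse is an inference from the reason for exit.
- *That the understatement reaches about 30% in relative terms.* This needs, for example, 15% exited with 40% 1-year mortality against 10% in the rest: 0.15 × 0.40 + 0.85 × 0.10 = 14.5%, and 4.5/14.5 = 31%. The implied hazard ratio is ln(0.6)/ln(0.9), about 4.8, for which the documents give no basis. The sum also ignores deaths before day 30, which Kaplan-Meier does capture.
- *That explanted patients leave at about day 30.* Their 30 days run from the explant and can be extended for related events. Someone explanted in year 2 is fully observed for 1-year mortality, so the day-30 model tends to overstate the 1-year gap for that group.
- *That the SAP bars a negative registry search from setting the censor date.* The sources listed in SAP 5.1.3 are examples. A negative search is neither named nor excluded, so the rule is merely unstated.

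It is also fair to say that non-implanted patients are censored only if mortality is analysed in ITT, which the documents do not settle. In the as-treated set they are missing altogether, so neither choice recovers their deaths.

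**Conclusion.** The point holds as a gap in data collection and analysis. Two groups exit because of device failure, the discretionary registry search does not name them, and mortality to 5 years is estimated as though their exit carried no information, with no sensitivity analysis. This also does not fit the statement in Protocol 6 that all enrolled patients are followed to 5 years.

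The likely size is modest: 0 to about 4 percentage points at 1 year under the assumed exit share, mortality and hazard ratio, against a sampling half-width of about 7-10 points at 65 patients. The true size, and strictly the direction, cannot be determined from the documents. The change is worth making because it is cheap and the information cannot be recovered by analysis later.

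The follow-up rules for explanted patients with unresolved events are a separate, narrow inconsistency. Protocol 7.4 sets no limit, 11.2 runs to resolution or a few other end points, and 11.8 stops at 180 days. It has little bearing on long-term mortality.

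**What to change.** **Protocol 7.4:** require, as consent allows, a vital-status or death-registry check at each annual analysis for every enrolled (skin-incision) patient who exits early, expressly including non-implanted and explanted patients, in place of a search at the sponsor's discretion.

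**SAP 5.1.3 and 8.2.2:** name ITT as a population for all-cause mortality. State how a search that finds no death sets the censor date. Report mortality with and without registry data, and give best- and worst-case bounds for patients whose status remains unknown.

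**Protocol 7.4, 11.2 and 11.8:** reconcile the passages on how long explanted patients with unresolved adverse events are followed.

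**Cost:** a sentence in the consent form and protocol, a few look-ups per year (about 3 to 10 patients under the assumed exit share), and no added visits. Registries may be incomplete, so a negative search is not proof of survival. The display with and without registry data lets the reader see how much depends on it.
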